12.6.2 Serious Adverse Events

An SAE is any untoward medical occurrence, in the view of either the investigator or sponsor, that:

- results in death
- is life-threatening
- results in inpatient hospitalization or prolongation of existing hospitalization
- results in persistent or significant disability/incapacity
- is a congenital anomaly/birth defect

Other important medical events that may not be immediately life-threatening or result in death or hospitalization, based upon appropriate medical judgment, are considered SAEs if they are thought to jeopardize the patient and/or require medical or surgical intervention to prevent 1 of the outcomes defining an SAE. SAEs are critically important for the identification of significant safety problems; therefore, it is important to take into account both the investigator's and the sponsor's assessment. If either the sponsor or the investigator believes that an event is serious, the event must be considered serious and evaluated by the sponsor for expedited reporting.

12.6.3 Serious Adverse Event Reporting

An SAE occurring from the time the patient gives informed consent until the end of the followup period (Day 60) or within 30 days of stopping the study drug (whichever is longer) must be reported to the Syneos Health Safety and Pharmacovigilance group and will be communicated to the sponsor. Any such SAE due to any cause, whether or not related to the study drug, must be reported within 24 hours the investigator's awareness of the event. Notification can be made using the dedicated fax line or email for the Syneos Health Safety and Pharmacovigilance group:

- Syneos Health Safety and Pharmacovigilance fax number: CC
- Syneos Health Safety and Pharmacovigilance email address:

If the investigator contacts the Syneos Health Safety and Pharmacovigilance group by telephone, then a written report must follow within 24 hours and has to include a full description of the event and sequelae in the format detailed in the SAE reporting form.

The event must also be recorded on the standard AE eCRF. Preliminary reports of SAEs must be followed up by detailed descriptions later on. Clear and anonymized photocopies of hospital case reports, consultant reports, autopsy reports, and other documents must be provided when requested by Syneos Health Safety and Pharmacovigilance. SAE reports must be made whether or not the investigator considers the event to be related to the investigational drug.

Appropriate remedial measures should be taken to treat the SAE, and the response should be recorded. Clinical, laboratory, and diagnostic measures should be employed as needed to determine the etiology of the problem. The investigator must report all additional follow-up

This document is confidential.

Page 64 of 80

MetrioPharm AG	MP1032-CT05
MP1032	Protocol v2.0 - France

evaluations to the Syneos Health Safety and Pharmacovigilance group within 24 hours of becoming aware of the additional information. All SAEs will be followed up until the investigator and sponsor agree the event is satisfactorily resolved.

Any SAE that is not resolved by the end of the study or upon discontinuation of the patient's participation in the study is to be followed up, if possible, until it either resolves, stabilizes, returns to baseline values (if a baseline value is available), or is shown to not be attributable to the study drug or procedures. It is understood that if a patient withdraws consent to further follow-up, then it may not be possible for the study site to follow the SAE to resolution.

12.6.4 Suspected Unexpected Serious Adverse Reactions

AEs that meet all of the following criteria will be classified as suspected unexpected serious adverse reactions (SUSARs) and reported to the appropriate regulatory authorities in accordance with applicable regulatory requirements for expedited reporting:

- serious
- unexpected (ie, the event is not consistent with the reference safety information in the current version of the IB)
- there is at least a reasonable possibility that there is a causal relationship between the event and the study drug

The investigator will assess whether an event is causally related to the study drug. Syneos Health will consider the investigator's assessment and determine whether the event meets the criteria for being reportable as a 7-day or 15-day safety report. SUSARs that are fatal or life-threatening must be reported to the regulatory authorities and the IRBs/IECs (where required) within 7 days after Syneos Health/MetrioPharm has first knowledge of them, with a follow-up report (when applicable) submitted within a further 8 calendar days. Other SUSARs must be reported to the relevant regulatory authorities and the IRBs/IECs within 15 calendar days after Syneos Health/MetrioPharm first has knowledge of them.

Syneos Health is responsible for reporting SUSARs and any other events required to be reported in an expedited manner to the regulatory authorities and for informing investigators of reportable events, in compliance with applicable regulatory requirements within specific timeframes. Investigators will notify the relevant IRBs/IECs of reportable events within the applicable timeframes.

If the investigator becomes aware of a pregnancy occurring in the partner of a patient participating in the study, the pregnancy should be reported to Syneos Health Safety and Pharmacovigilance group within 24 hours of knowledge of the event. Information regarding the pregnancy must only be submitted after obtaining consent from the pregnant partner. The investigator will arrange counseling for the pregnant partner by a specialist to discuss the risks of continuing with the pregnancy and the possible effects on the fetus.

Upon discontinuation from the study drug, only those procedures that would not expose the patient to undue risk will be performed. The investigator should also be notified of pregnancy occurring during the study but confirmed after completion of the study. In the event, that a patient is subsequently found to be pregnant after inclusion in the study and received at least one dose of study drug, any pregnancy will be followed to term, and the status of mother and child will be reported to Syneos Health Safety and Pharmacovigilance group after delivery.

12.6.6 Overdose

The investigator must immediately notify Syneos Health of any occurrence of overdose with the study drug.

B PHARMACOKINETICS

B1 Pharmacokinetic Sampling

Blood samples for PK analysis of MP1032 plasma concentrations will be collected at the time points indicated in the Schedule of Assessments (Table 1) from a PK subset of approximately 30 patients (who give optional consent). In summary, PK samples will be collected via sparse sampling from these 30 patients (approximately) in a 2:1 ratio (approximately 20 patients from the 300 mg MP1032 BID plus SoC group and approximately 10 patients from the placebo group plus SoC group) to assess the PK of MP1032 on Day 1 (single dose) and Day 7 (steady state). A

This document is confidential.

Page 66 of 80

total of 16 samples (approximately 4.9 mL per time point for a total of approximately 78.4 mL) will be collected relative to the first dose on Day 1 and the first dose on Day 7. Samples on Day 1 and Day 7 will be collected predose (within 10 minutes before the first daily dose) and postdose at 10 minutes, 20 minutes, 30 minutes, 60 minutes, 120 minutes, 8 hours (before next dose), and 24 hours before the next morning dose (if applicable), if possible. Patients who provide consent for the PK sampling, but are no longer hospitalized on Day 7, will not have Day 7 PK samples collected.

For patients in the PK subset on Day 1 and Day 7 only: Patients should not eat within the 4 hours before planned study drug administration and within the 120 minutes after study drug dosing, when feasible. Thus, study drug should be administered in fasted state (\geq 4 hours), when feasible. However, if a patient has eaten within the 4 hours before their planned administration, study drug dosing may proceed. The patient's fed or fasted state, as well as food intake (yes/no) within the 120 minutes after study drug dosing should be recorded. The PK samples should be collected as planned regardless of the patients' fasted/fed state. The study site should record the date and time of dosing (recorded as the time when the first capsule is administered).

Intravenous cannulas may be used for blood collection to avoid multiple skin punctures, when appropriate. Otherwise, blood samples will be collected by direct venipuncture. The actual date and time of each blood sample collection will be recorded. Sample collections completed outside the predefined time windows (windows to be specified in the laboratory manual) will not be considered as protocol deviations because actual postdose sampling times will be used for PK and statistical analyses.

PK samples will be analyzed by a central laboratory facility (Prolytic GmbH). Details of PK blood sample collection, processing (including separation of plasma), storage, and shipping procedures will be provided in a separate laboratory manual.

B.2 Pharmacokinetic Analytical Methodology

The concentration of study drug will be determined from the plasma samples using a validated analytical method. Details of the method validation and sample analysis will be included with the final clinical study report (CSR).

14 OTHER ASSESSMENTS

14.1 Biomarkers

Blood samples will be obtained at the visits specified in the Schedule of Assessments (Table 1) on Day 1 (before the first study drug administration) and Days 7, 14, 21, 28, and 60 (when possible) to measure biomarkers levels. Blood samples for biomarkers must be collected on Days 7, 14, 21, 28, and 60 if a patient is still hospitalized. If a patient is discharged, the study site should arrange an outpatient visit (ie, at the study site) to accommodate the collection of blood samples for biomarkers on Days 7, 14, 21, 28, and 60.

This document is confidential.

Page 67 of 80

MetrioPharm AG	MP1032-CT05	
MP1032	Final	
MetrioPharm AG	MP1032-CT05	
MP1032	Protocol v2.0 - France	

Biomarkers will potentially include, but will not be limited, to cytokines (eg, C-reactive protein, IL-1 β , IL-6, TNF- α , and IFN- γ) and other coagulation/inflammatory biomarkers (eg, D-dimer and ferritin). Samples may be collected at the same time that samples are collected for the clinical laboratory assessments. Blood samples will be analyzed by a central laboratory facility. Details of sample collection, processing, storage, shipping procedures, and analysis will be provided in a separate laboratory manual.

Please note: Patients will be requested to provide consent for the sponsor to store and use leftover blood samples for future exploratory biomarker research. Patient participation in the storage and use of leftover blood samples is optional. If the patient consents, the sponsor will store and use the leftover blood samples for a period of 3 years after the last patient has completed his/her last visit in this study.

5 STATISTICAL ANALYSIS

The statistical analysis plan (SAP) will provide further details regarding the definition of analysis variables and analysis methodology to address all study objectives. The SAP will be finalized before any statistical output (eg, DSMB output) is produced. The SAP will serve as a companion document to the protocol. The SAP will further describe the statistical analyses. All data will be included with the final CSR.

The statistical evaluation will be performed using SAS® software version 9.4 or higher

(CCI[®]CCI).

Summary statistics will be presented by treatment group. Continuous and ordinal variables will be summarized by the number of patients (N), mean, standard deviation, median, minimum, and maximum for actual values and change from baseline. Additionally, for ordinal data, the number and percentage of patients in each category will be presented. Binary and categorical variables will be summarized for each treatment group by presenting the number and percentage of patients in the categories.

Statistical tests for comparison between treatments will be performed using a two-sided alpha level of 10%. No adjustment for multiple testing will be applied in this descriptive proof-of-concept study.

151 Determination of Sample Size

The primary efficacy endpoint "proportion of patients with disease progression on Day 14" is assumed to be 10% in the 300 mg MP1032 BID plus SoC treatment group (Arm A) and 30% in the placebo plus SoC treatment group (Arm B). Using the Chi-square test with type I error alpha=10% two-sided for this proof-of-concept study and 2:1 randomization ratio, with 114 randomized patients (76 in Arm A and 38 in Arm B) a statistical power of 83% can be achieved. Considering about 5% early study terminations, the necessary sample size to randomize results is 120 patients in total (80 in Arm A and 40 in Arm B). If during the conduct

This document is confidential.

Page 68 of 80

MetrioPharm AG	MP1032-CT05
MP1032	Protocol v2.0 - France

of the study the early study termination rate is higher than the estimated 5%, then an increase in the randomized number of patients may be necessary.

Sample size estimation was performed using nQuery 8, Version 8.6.1.0.

A subset of randomized patients will be consented for the collection of blood samples for PK measurements. The PK subset consists of approximately 20 patients from the 300 mg MP1032 BID plus SoC group and approximately 10 patients from the placebo plus SoC group, up to a total of approximately 30 patients.

15.2 Analysis Sets

Screened Set

The Screened Set will include all patients who give informed consent and are screened. For this group, patient disposition, and reasons for premature study termination or screening failure will be described.

Randomized Set

The Randomized Set will include all patients randomized. Unless specified otherwise, this set will be used for all subject listings with exception of the listing presenting screening failures and the respective reason(s) for screen failure.

Intention-To-Treat Set

The Intention-To-Treat (ITT) set, correspond with randomized set, will include all randomized patients irrespective of any deviation from the protocol or premature discontinuation from study drug/withdrawal from study. The treatment group assignment will be designated according to initial randomization. The ITT will serve as the basis for the analysis of efficacy and summary of demographics and baseline characteristics.

Per Protocol Set

The Per Protocol Set (PPS) will include all patients from ITT who received at least 1 dose of study drug and who do not have any major protocol deviations impacting the efficacy assessments. The PPS will be used for supportive analyses of efficacy.

Safety Set

The Safety Set (SS) will include all randomized patients who receive at least 1 dose of study drug. The treatment group assignment in the SS will be defined by the treatment actually received. The SS will be used for the analysis of safety.

PK Analysis Set

The PK Analysis Set (PKS) will include all the patients who have been administered active study drug and have at least 1 postdose evaluable plasma concentration after Day 1 dose.

This document is confidential.

Page 69 of 80

5.3 Efficacy Analysis

The estimands for the primary efficacy endpoint and for the 4 key secondary endpoints comparing the 2 treatment groups will be tested with consideration of a two-sided type-1 error alpha of 10% for each test on the ITT. Additionally, 95% confidence intervals will be provided. Also, the treatment comparison with regards to the other secondary efficacy endpoints will be performed using a two-sided alpha level of 10%.

The main estimand for the primary efficacy endpoint is defined as follows:

- Treatment: 300 mg MP1032 BID plus SoC in Arm A and placebo BID plus SoC in Arm B. If a patient terminates the study drug, but still remains in the study and is followed up, then the patient will continue to receive either SoC alone or SoC+ additional treatment. These treatments are defined with regards to intercurrent events as 'other treatments'.
- Population: Of all patients defined by the study inclusion/exclusion criteria, the analysis population will include patients who were randomized to study drug (ITT population).
- Variable: A binary variable indicating disease progression (death or respiratory failure) at Day 14. Respiratory failure is defined as patients who have a score of 2, 3, or 4 on the NIAID 8-point ordinal scale.
- Intercurrent events: All events that lead to study drug discontinuation and/or switch to other treatment before Day 14 will be handled using the treatment-policy strategy (ie, the NIAID score at Day 14 will be used for definition of the failure in such patients).
- Population-level summary: Common risk difference resulting from the Mantel-Haenszel (MH) test considering the 4 strata out of the combinations of the 2 randomization stratification factors disease severity (moderate versus severe) and ageclass (aged ≤65 years versus >65 years) at baseline.

Missing data on Day 14 resulting from study termination before Day 14 are not expected. However, in case they happen, such monotone missings will be imputed by multiple imputation using information from similar patients of the same treatment group. Missing post-baseline data for patients randomized but not treated will be imputed by the respective baseline value (baseline observation carried forward [BOCF]). They comparison between the treatment groups will be performed on the ITT after imputation of missing values using MH test for common risk difference considering the 4 strata resulting from the 2 randomization stratification factors disease severity (moderate versus severe) and age-class (aged ≤ 65 years versus > 65 years). The 95% confidence intervals will be provided for the risk difference.

Similar MH analyses and presentation of 95% confidence intervals will be applied to the main estimand of the first key secondary efficacy endpoint, which is defined as a binary variable indicating disease progression (death or respiratory failure) at Day 28, and the main estimand of the second key secondary efficacy endpoint that is defined as a binary variable indicating disease resolution (alive and have a score of 6, 7 or 8 on NIAID) at Day 28. Intercurrent events that lead to study drug discontinuation and/or switch to other treatment before Day 28 will be handled

This document is confidential.

Page 70 of 80

MetrioPharm AG	MP1032-CT05	
MP1032	Final	
MetrioPharm AG	MP1032-CT05	
MP1032	Protocol v2.0 - France	

using the treatment-policy strategy for these 2 estimands (ie, the NIAID score at Day 28 will be used for definition of the failure or response, respectively) in such patients. Missing data on Day 28 will be imputed by multiple imputation using information from similar patients of the same treatment group. Missing post-baseline data for patients randomized but not treated will be imputed by BOCF.

A similar MH approach and presentation of 95% confidence intervals as described above will be applied also to the main estimand of the third key secondary efficacy endpoint, which is the all-cause mortality at Day 28. Intercurrent events that lead to study drug discontinuation and/or switch to other treatment before Day 28 will be handled using the treatment-policy strategy (ie, the life status at Day 28 will be considered). No missing data of life status on Day 28 is expected.

The main estimand of the fourth key secondary efficacy endpoint, change of clinical status related to COVID-19 on Day 28 compared with baseline according to the NIAID 8-point ordinal scale, will be compared using the risk difference from the analysis of covariance model with treatment and the 2 binary stratification factors (eg, severity and age-class) as independent factors and the baseline value of NIAID as independent covariate. Intercurrent events that lead to study drug discontinuation and/or switch to other treatment before Day 28 will be handled using the treatment-policy strategy for this estimand (ie, the NIAID score at Day 28 will be used). Missing data on Day 28 will be imputed by multiple imputation using information from similar patients of the same treatment group. Missing post-baseline data for patients randomized but not treated will be imputed by BOCF. The 95% confidence intervals will be provided for the risk difference.

The population for all above described estimands of the key secondary endpoints is the ITT.

Sensitivity analyses for the main endpoints of the primary and key efficacy estimands will be performed by assuming missing data at Day 14 or Day 28 as failure or non-resolution for the binary endpoints, and by multiple imputation using information from similar patients of the placebo group for the NIAID 8-point ordinal scale.

All above analyses for the main estimands of the primary efficacy and key secondary efficacy endpoints will be repeated on PPS as supportive analysis. Additionally, for the primary efficacy and binary key secondary efficacy endpoints logistic regression model with treatment and the 2 stratification factors as covariables will be performed on the ITT. Further estimands for the primary and key secondary efficacy endpoints will be provided in the SAP.

The proportion of patients with disease resolution at Day 14 and the all-cause mortality rate at Day 14 and Day 60 will be analyzed using similar MH methods as described above for Day 28. Cumulative proportion of patients with disease resolution will be plotted by time.

A similar analysis of covariance approach as described above for Day 28 will be applied for the analysis of the change of clinical status related to COVID-19 on Day 14 compared with baseline on the NIAID 8-point ordinal scale. The endpoint considering the proportion of patients requiring invasive ventilation (mechanical ventilator and/or ECMO) or who are not alive, the

This document is confidential.

Page 71 of 80

MetrioPharm AG MP1032

proportion of patients in each NIAID category, and the proportion of patients alive and testing negative for COVID-19 on Day 14, Day 28, and Day 60, respectively, will be compared between the treatment groups using MH test. Overall survival, time to (first) improvement of at least 1 category on the NIAID scale and total hospitalization duration (from baseline to discharge; with death censored on last day of the observed period – at Day 28 or Day 60, respectively – depending on the analyses) will be summarized using the Kaplan-Meier method and will be compared between treatment groups using log-rank tests. Additionally, Cox proportional hazards model will be applied with treatment and the 2 stratification factors as covariables.

The odds ratio between MP1032 and SoC and placebo and SoC for the number of patients with clinical status improvement from baseline on the NIAID 8-point ordinal scale (ie, an improvement of at least 1 category) at Day 14 and Day 28 will be analyzed using a logistic regression with consideration of the 2 stratification factors.

The time to recovery of all at baseline present COVID-19 symptoms (stuffy or runny nose, sore throat, red or irritated eyes, shortness of breath, cough, low energy or tiredness, muscle or body aches, headache, chills or shivering, feeling hot or feverish, nausea, and number of times of vomit, times of diarrhea, sense of smell, sense of taste in the last 24 hours) will be presented by Kaplan-Meier estimates and figure. The change from baseline will be presented in shift tables for each single symptom, with the number and percentage of subjects in each category at post-baseline assessment time-point compared to baseline for each treatment group.

Total number of days in ICU, duration of invasive mechanical ventilation, and duration of ECMO will be descriptively summarized by treatment group using mean days with 90% confidence intervals and additionally by median days and quartiles. To consider death sufficiently unfavorable in these measures, in case of death the duration of the respective measure will be considered with the longest duration possible (eg, if a summary of the first 28 days is presented, then death before Day 28 will be considered as duration 28 days, and if the summary also includes follow-up period until Day 60, then death before Day 60 will be considered as duration of 60 days). Both summaries (up to Day 28 and up to Day 60) will be provided.

For HRQoL assessments at discharge and Day 60, the EQ index value and the EQ VAS, both based on the EQ-5D-5L questionnaire will be calculated and summarized by visit and treatment group. Additionally, change at Day 60 from discharge will be summarized by treatment group.

All efficacy endpoints will be summarized using descriptive statistics by treatment group and by visit, as appropriate: Binary and categorical endpoints will be summarized by treatment group by presenting the number and percentage of patients in the categories. Continuous and ordinal endpoints will be described by mean, standard deviation, median, minimum, and maximum for actual values and change from baseline. Additionally, for ordinal data, the number and percentage of patients in each category will be presented.

This document is confidential.

Page 72 of 80

MetrioPharm AG	MP1032-CT05
MP1032	Protocol v2.0 - France

MP1032-CT05

Final

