5 INTRODUCTION

51 Background on COVID49

On 31 December 2019, the World Health Organization (WHO) was informed of a cluster of cases of pneumonia of unknown cause detected in **CC** . Severe acute respiratory syndrome coronavirus type 2 (SARS-CoV-2) was identified as the causative virus by Chinese authorities on 07 January 2020 (WHO 2020a). Coronavirus disease 2019 (COVID-19) was identified as the disease caused by SARS-CoV-2 infection. In March 2020, the COVID-19 outbreak was declared as a pandemic by the WHO. The disease resulting from SARS-CoV-2 led to shutdowns and social measures in great parts of the world, particularly to slow down the transmission of the virus and thereby avoiding the overburden of health care systems.

The pandemic is still ongoing. Estimates of actual morbidity, mortality, and lethality are highly variable and depend on factors such as the time of analysis, region analyzed, and surveillance methods. As of 04 August 2020, the WHO estimated the case fatality ratio, which estimates the proportion of deaths among confirmed cases, to vary from 0.1% to >25%. Whereas, the true severity of COVID-19 as measured by the infection fatality ratio, which estimates the proportion of deaths among all infected individuals, is estimated to be approximately 0.5% to 1% (WHO 2020b). In a more recent summary of Levin et al (2020) it could be clearly shown that the infection fatality ratio is highly age dependent, being in average as low as 0.004% for patients younger than 35 and as high as 28.3% in patients at the age of 85 and older.

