2 SAFETY ASSESSMENTS

Safety assessments (medical/surgery history, demographics, prior and concomitant medications, vital signs, physical examinations, ECGs, clinical laboratory assessments, and AEs) are to be performed at the visits specified in the Schedule of Assessments (Table 1).

121 Medical/Surgical History and Demographics

Medical/surgical history will be recorded at screening. Investigators will document all active and chronic diseases (eg, asthma and COPD), and any diseases diagnosed in the past 1 year (before

This document is confidential.

Page 58 of 80

MetrioPharm AG
MP1032

screening) that the investigator considers clinically significant. Additional pre-existing conditions present at the time when informed consent is given and up to the time of first dosing (Day 1) are to be regarded as concomitant. Medical history will include documentation of social behaviors, including use of tobacco, nicotine (including use of electronic cigarettes), and soft or hard drugs (including cannabis), as well as alcohol consumption, if applicable. Smoking history also must be documented as part of medical history and includes: never, light (<100 cigarettes/lifetime), active smoker, and former smoker (quit date). History of number packs/day, number of smoking years, and quitting time for former and active smokers must also be documented.

Additionally, the investigators will document at screening the patient's Charlson score via the Charlson Comorbidity Index (Charlson et al 1987). The Charlson Comorbidity Index may be used to identify patients with higher risk of COVID-19 progression (Garibaldi et al 2020) via the COVID-19 Inpatient Risk Calculator (online calculator available via: https://rsconnect.biostat.jhsph.edu/covid_predict/). The 14-item Charlson score is based on the

patient's comorbidities that are associated with mortality: myocardial infarction, congestive heart failure, peripheral vascular disease, cerebrovascular disease, dementia, chronic pulmonary disease, rheumatologic disease, peptic ulcer disease, liver disease, diabetes, hemiplegia or paraplegia, renal disease, malignancy, and acquired immunodeficiency syndrome/human immunodeficiency virus (online calculator available via: https://www.orthotoolkit.com/charlson-comorbidity-index/). The investigator should record each individual component of the 14-item Charlson Comorbidity Index as well as the overall score.

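### The ANCOVA models for change in NIAID status adjust for age only as ≤65 versus >65; this is valid, but continuous age would recover some precision at the cost of one parameter

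*Protocol*

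**What the plan says.** Protocol Section 15.3 (same text in the Bulgarian and French versions) analyses the fourth key secondary endpoint, change in NIAID status at Day 28, with an "analysis of covariance model with treatment and the 2 binary stratification factors (eg, severity and age-class) as independent factors". The baseline NIAID score is a further covariate. A similar ANCOVA is planned for Day 14. The logistic models use treatment and the same two factors. For the time-to-event endpoints, log-rank tests are the comparison and, in addition, a "Cox proportional hazards model will be applied with treatment and the 2 stratification factors as covariables".

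The age factor is the randomization stratum of Section 9.3.1, ≤65 versus >65 years. The primary endpoint and the three binary key secondary endpoints are analysed by Mantel-Haenszel over the four strata; the logistic models for them are supplementary.

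On age as a risk factor, Section 5.1 reports that the "infection fatality ratio is highly age dependent, being in average as low as 0.004% for patients younger than 35", rising to 28.3% at 85 and older. Age is recorded for all patients (Section 12.1 and Table 1). Section 12.1 also has the Charlson score recorded and says that the "Charlson Comorbidity Index may be used to identify patients with higher risk of COVID-19 progression". Neither exact age nor the Charlson score enters any efficacy model in the protocol.

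**The concern.** Eligibility starts at 18 years with no upper limit. A single cut at 65 therefore treats a 20-year-old and a 65-year-old as equal, and likewise a 66-year-old and an 88-year-old. If the NIAID change depends on age within those classes, that part of the age effect stays in the residual variance of the ANCOVA and widens the interval for the treatment difference.

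The covariate set is written into the protocol itself, so it is not a detail left for the SAP. What is at stake is precision in the one main analysis, among the primary and four key secondary endpoints, that is model-based. Baseline NIAID is unlikely to stand in fully for age: all patients are hospitalized and critical disease is excluded, so baseline scores should fall mostly in categories 4 and 5 and overlap with the severity factor.

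**Working it through.** **1. The protocol's own figure.** Section 15.1 gives the inputs: "Using the Chi-square test with type I error alpha=10% two-sided for this proof-of-concept study and 2:1 randomization ratio", rates "assumed to be 10% in the 300 mg MP1032 BID plus SoC treatment group (Arm A) and 30% in the placebo plus SoC", with "76 in Arm A and 38 in Arm B", and concludes that "a statistical power of 83% can be achieved".

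- Pooled rate: (76×0.10 + 38×0.30)/114 = 19/114 = 0.1667.
- Standard error under the null: √[0.1667×0.8333×(1/76 + 1/38)] = 0.0740.
- Standard error under the alternative: √(0.10×0.90/76 + 0.30×0.70/38) = 0.0819.
- Power: Φ[(0.20 − 1.645×0.0740)/0.0819] = Φ(0.955) = 83.0%.

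The stated 83% reproduces, and 114/0.95 = 120. The calculation is for an unadjusted chi-square test, so the covariate choice does not affect it.

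**2. Age information kept by the split.** The protocol gives no age distribution. Assume a normal distribution with SD 15 and mean 55, 60 or 65, and a linear age effect. With c = (65 − mean)/15, P = 1 − Φ(c) and φ the normal density, the share of linear age information kept is R = φ(c)²/[P(1−P)].

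- Mean 55: R = 0.541.
- Mean 60: R = 0.611.
- Mean 65: R = 0.637.

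**3. Effect on the ANCOVA.** For an age-outcome correlation ρ, the residual variance with age-class relative to continuous age is (1 − Rρ²)/(1 − ρ²). Example at mean 60 and ρ = 0.3: (1 − 0.611×0.09)/0.91 = 1.038. The equivalent number of patients is 120×(ratio − 1).

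| ρ | Excess residual variance | Patients of 120 |
|---|---|---|
| 0.2 | 1.5-1.9% | about 2 |
| 0.3 | 3.6-4.5% | 4-6 |
| 0.4 | 6.9-8.7% | 8-11 |
| 0.5 | 12-15% | 15-18 |

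Here ρ should be read as what remains after severity and baseline NIAID. The protocol gives nothing from which to estimate that.

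**4. Chance age imbalance.** The standard error of the between-arm difference in mean age is SD×√(1/80 + 1/40). Without stratification this is 15×0.194 = 2.9 years. Within age-class the SD is 15×√(1 − R) = 9.0 to 10.2 years, which gives 1.8 to 2.0 years.

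**5. Logistic model.** Simulation with 114 patients, 2:1 within strata, 10% versus 30%, mean age 60, and 2,000 trials per scenario (Monte Carlo standard error about 0.8 points per figure):

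| OR per 10 years | Power, age-class | Power, continuous age | Variance ratio, adjusted risk difference |
|---|---|---|---|
| 1.35 | 85.1% | 85.3% | 1.01 |
| 1.65 | 86.3% | 87.4% | 1.03 |
| 2.2 | 88.9% | 89.5% | 1.04 |
| 4.95 | 91.8% | 95.9% | 1.17 |

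The last row has a slope of 0.16 per year, about what the cited fatality ratios imply: [logit(0.283) − logit(0.00004)]/(50 to 60 years) = 9.20/(50 to 60) = 0.15 to 0.18. With no treatment effect and OR 1.65, the rejection rates were 10.1% (age-class) and 10.3% (continuous), both close to the nominal 10%.

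Gains for the Cox models and for the Charlson score were not computed, because the protocol gives no event rates or effect sizes for them.

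**The case against.** Adjusting for the factors used to stratify randomization is a standard and valid choice. The test keeps its level, nothing in the protocol is contradicted, and the study is described as a proof of concept. The ANCOVA already adjusts for baseline NIAID, which may absorb part of the age effect. The assumed linear effect favours continuous age. The cited fatality gradient concerns death among all infected people, not NIAID status at Day 14 or 28 in inpatients without critical disease, so the relevant slope is probably flatter. An unseen SAP may add a sensitivity model with continuous age. All of this stands and limits the size of the gain. It does not remove the point that the protocol fixes a coarser covariate than the data allow in a main analysis.

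Three stronger readings are tempting, and the documents do not support them.

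- A reader might infer that chance age imbalance goes uncorrected. Imbalance across 65 is handled by the stratified randomization, the Mantel-Haenszel strata and the age-class term. Only imbalance within each class remains; it is random, and it adds noise rather than bias.
- A reader might infer that the primary, mortality and survival comparisons suffer in the same way and would be repaired. Their main analyses are Mantel-Haenszel and log-rank, which a model covariate does not touch.
- A reader might infer that the Charlson score should be added too. The protocol says only that it may help to identify patients at higher risk, and there is no figure from which to judge a gain.

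**Conclusion.** The point holds for the ANCOVA models at Day 28 and Day 14, as a matter of efficiency. Under an assumed age SD of 15, mean 55 to 65 and a linear effect, the two-level factor costs about 2% to 9% in residual variance at age-outcome correlations of 0.2 to 0.4, and 12% to 15% at 0.5. Any part of the age effect that baseline NIAID already carries reduces these figures.

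For the logistic models the gain is about 0 to 1 point of power at slopes plausible for inpatients. It reaches about 4 points only near the gradient for all infected people. About 19 primary events are expected (7.6 + 11.4), so there is little room for extra terms, and an added covariate changes the conditional odds or hazard ratio without necessarily narrowing its interval. The precision argument therefore applies cleanly to the ANCOVA and to standardised risk differences only.

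The planned analyses remain valid and the 83% power statement is correct. This is a free improvement, not an error.

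**What to change.** In Section 15.3, prespecify age at baseline as a continuous covariate in the Day 28 and Day 14 ANCOVA models, alongside treatment, severity, age-class and baseline NIAID. Keep ≤65 versus >65 for randomization and for the Mantel-Haenszel strata. In the supportive logistic and additional Cox models, continuous age is optional; if it is used, state that the odds or hazard ratio is conditional on age.

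The cost is one model term, with no new data collection. The present ANCOVA has five parameters (intercept, treatment, severity, age-class, baseline NIAID), so the change uses 1 of 120 − 5 = 115 residual degrees of freedom. That is a price of the order of 1/115 = 0.9% in variance, which takes up part of the gain if the correlation is only 0.2. The choice should be made before unblinding, because adding age afterwards would look data-driven.
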